7.4.6.2 Permitted Medications

Other than medications specifically prohibited in this study, subjects may receive concomitant medications as required. Medications (prescription, over-the-counter, and herbal) and nutritional supplements taken during the 30 days prior to Screening will be reviewed and recorded at the Screening visit. At the Baseline visit, current medications will be recorded. At each visit, any concomitant medications added or discontinued during the study should be recorded on the CRF.

The site personnel should record the following in the CRF: date and time the medication was taken, the name of the medication, and the reason the medication was taken.

7.4.7 Treatment Compliance

Site personnel will maintain a record of all medication dispensed to each subject. Subjects will be instructed to bring all unused study drug and product packaging to every visit. Drug accountability will be assessed by site personnel and recorded. All used containers and unused study drug must be returned at in-clinic visits. Measurements of trough free SA levels in the serum and urine may also analyzed to provide an estimate of treatment compliance in this study.

7.5 Study Procedures and Assessments

The individual indicated in each scale description will perform all assessments listed below. Whenever possible, study site staff (including trained clinicians, physical therapists, and the Investigator or site designee) performing the assessments should be consistent from visit to visit throughout the study.

The parameters to be assessed in Study UX001-CL301, along with timing of assessments, are provided in the Schedule of Events ([Table 2.1](#)). Refer to the Study Reference Manual for additional details on specific assessments and the suggested order of administration.

7.5.1 Study Schedule

The Schedule of Events ([Table 2.1](#)) details all procedures to be completed at each visit and should serve as the primary section of the protocol regarding visit-specific study procedures.

7.5.1.1 Screening Period

Informed consent must be obtained prior to any Screening procedures. Screening procedures may take place across multiple days to allow enough time to complete all procedures and confirm initial subject eligibility. Screening procedures and dates should be well documented in the source documents and CRF. The date of the Screening Visit is the date the patient has signed informed consent for this study.

7.5.1.2 Baseline Visit

The Baseline (Week 0) visit should take place within 7 to 28 days of the Screening visit. Subjects will be randomized only after inclusion/exclusion criteria have been confirmed. Baseline visit (Week 0) assessments must be completed prior to first dose of study drug.

7.5.1.3 Treatment Period

Subjects will be contacted by telephone four weeks after the Baseline Visit for an abbreviated safety follow-up. Subjects will return to the clinic at 8-week intervals (± 5 days) throughout the Treatment Period (Weeks 0 – 48).

7.5.1.4 End of Study/Early Termination Visit (Week 48/ET)

All randomized subjects who complete the study or discontinue early should complete the Week 48/ET visit.

For subjects who discontinue prior to completing the 48-week Treatment Period, every reasonable effort should be made to perform the Early Termination Visit procedures within four weeks of discontinuation.

7.5.1.5 Safety Follow-up Period

A safety follow-up call should be initiated by the site personnel 28 days (+5 days) after a subject's last dose of study drug to collect information on any ongoing or new AEs, serious adverse events (SAEs), and concomitant medications. Appropriate follow-up should continue until all safety concerns, in the Investigator's opinion, are resolved.

This call should be completed only for subjects who complete the study and choose not to enroll in the extension study, UX001-CL302, or who discontinue the study early.

Subjects who have completed the Week 48 Visit of this study, meet the requirements of the extension study, and choose to enroll in the open-label extension study, UX001-CL302, will not be required complete the follow-call.

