SUICIDAL IDEATION AND BEHAVIOR ^j	X	X		X	X	X	X	X	X	

ASSESSMENTS AND EVENTS*	SCREENING ^a	BASELINE ^a	TREATMENT PERIOD ^b							SAFETY FOLLOW-UP ^c
	WEEK -4 to -1	0	4 (TC)	8	16	24	32	40	48/ET ^a	52 (TC)
ADVERSE EVENTS	X	X	X ^b	X	X	X	X	X	X	X
TREATMENT DISPENSED ^k		X		X	X	X	X	X		
TREATMENT COMPLIANCE				X	X	X	X	X	X	

* Refer to Study Reference Manual for recommended timing and order of assessments to be administered at each study visit

- a. Potential subjects will be screened approximately seven days (up to 28 days) before the Baseline Visit. Study drug will be dispensed only after all study procedures at the Baseline Visit have been performed. For subjects who discontinue prior to completing the study, every reasonable effort should be made to perform the Early Termination (ET) procedures within four weeks of discontinuation.
- b. Visits occur every 8 weeks ± 5 days; subjects will be contacted by telephone call (TC) at Week 4 for abbreviated safety assessment. Additional unscheduled telephone calls may also occur for subject follow up. Unscheduled visits are allowed for safety or administrative purposes. Notify the medical monitor before an unscheduled visit.
- c. To be completed only for subjects who complete the study and choose not to enroll in the extension study, UX001-CL302, or who discontinue the study early. This call is not required for subjects who are eligible and choose to take part in the extension study, UX001-CL302. The site personnel will initiate a safety follow-up telephone call 28 days (+5 days) after a subject's last dose of study drug to collect information on any ongoing or new AEs, serious adverse events (SAEs), and concomitant medications. Appropriate follow-up should continue until all safety concerns, in the Investigator's opinion, are resolved.
- d. Medical history will include a detailed GNEM disease-specific medical history.
- e. CGI-Severity scale will be assessed at Baseline (Week 0) along with identification of 3 target areas for disease improvement; CGI-Improvement scale will be assessed at each subsequent visit using 3 target areas identified at Baseline.
- f. Pre-dose blood samples and first-morning void urine will be collected to assess trough SA levels; record volume of urine collected.
- g. An aliquot from the urine sample provided for the standard urinalysis will be used for assessment of ManNAc.

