7.4.3 Selection of Doses and Study Duration

Selection of Doses:

Successful use of SA replacement therapy in humans is believed to depend upon optimized exposure to the compound in the bloodstream to drive uptake of SA into the muscle. The 6 g/day SA-ER dose was selected based on biochemical and clinical data collected to date showing that 6 g/day is an efficacious dose, that 3 g/day is not efficacious, and that a higher dose of 12 g/day did not result in a significant improvement in effect over 6 g/day. These data derive from a randomized, placebo-controlled Phase 2 study and a corresponding extension study.

The Phase 2, randomized, placebo-controlled study (UX001-CL201) evaluated treatment with SA-ER at two dose levels of 3 g/day and 6 g/day for 48 weeks. In this study, the higher dose of 6 g/day stabilized upper extremity muscle strength compared with placebo or the lower 3 g/day dose; this finding was supported by measurements of functional outcome on the GNEM-FAS indicating the difference in muscle strength was clinically meaningful to subjects.

A higher 12 g/day dose administered as 1.5 g SA-ER and 1.5 g SA-IR orally four times daily was evaluated in Part II of the Phase 2 extension study (UX001-CL202) in existing subjects who transitioned from 6 g/day to 12 g/day, and in 13 treatment-naïve subjects who initiated SA treatment at 12 g/day. No substantial or dramatic additional efficacy benefit was conveyed by the 12 g/day dose over the 6 g/day dose. The safety of the 12 g/day dose appeared generally similar to 6 g/day but with a notable increase in GI symptoms, including flatulence.

Given these biochemical and clinical results, the 6 g/day SA-ER dose has been selected for further study as the minimum effective dose with a maximal or near maximal treatment effect that will provide the best opportunity for efficacy in all subjects with a good safety profile.

Study Duration:

Individual subject participation in this study will be a maximum of 56 weeks, including up to 4 weeks between Screening and Baseline visits, a treatment duration of 48 weeks, and a Safety Follow-up Call occurring approximately 4 weeks after last study drug administration. Subjects who complete the study may be eligible to participate in an open-label extension study.

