7.5.5.10 Adverse Events

All AEs will be recorded from the time the subject signs the informed consent until 30 days after the last dose of study drug, or, if applicable, until the date the subjects signs the informed consent for the open-label extension study, UX001-CL302, whichever occurs sooner.

The determination, evaluation, reporting, and follow-up of AEs will be performed as outlined in Section 8.5. At each visit subjects will be asked about any new or ongoing AEs since the previous visit. Assessments of AEs will occur at each study visit.

Clinically significant changes from study baseline in interval history, physical and neurological examination findings, vital signs, weight, clinical laboratory parameters, and concomitant medications will be recorded as AEs or SAEs, if appropriate.

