8.5.4 Adverse Event Reporting

8.5.4.1 General

All AEs (i.e. any new or worsening in severity or frequency of a preexisting condition) with onset after the subject signs consent for study participation must be promptly documented on the CRF. The Principal Investigator is responsible for evaluating all AEs, obtaining supporting documents, and ensuring documentation of the event is adequate. Details of the AE must include severity, relationship to study drug, duration, and outcome.

All AEs will be collected from the time the subject signs the informed consent through 30 days following the last dose of study drug, or, if applicable, until the date the subject signs

the informed consent for the open-label extension study, UX001-CL302, whichever occurs sooner. In addition for those subjects choosing not to enroll in UX001-CL302, the Investigator should report any AE that occurs more than 30 days following the last dose of study drug that is believed to have a reasonable possibility of being associated with study drug.

AEs ongoing after the defined follow-up period stated in the paragraph above should have a comment in the source document by the Investigator that the event has recovered, recovered with sequelae, or stabilized.

8.5.4.2 Serious Adverse Events, Serious Adverse Drug Reactions, and Requirements for Immediate Reporting

Ultragenyx or its designee must be notified of the occurrence of any SAE that occurs during the reporting period within 24 hours of the Investigator, designee, or site personnel's knowledge of the event. SAEs will be reported by completing and submitting SAE report forms to Ultragenyx or designee.

Follow-up SAE information must be submitted in a timely manner as additional information becomes available. All SAEs regardless of relationship to study drug must be followed to resolution or stabilization if improvement is not expected.

All deaths, regardless of causality, occurring from signing of the informed consent through the defined follow-up period stated in Section 8.5.4.1 are to be reported as SAEs to Ultragenyx or its designee within 24 hours of knowledge.

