## 8.9 Safety Analyses

Analysis of safety will be performed on the safety analysis set. Blinded study data will be monitored on an ongoing basis by the clinical study team including the medical monitor and the clinical drug safety team to ensure patients' safety.

Safety will be evaluated by the incidence, frequency and severity of AEs and SAEs, including clinically significant changes from study baseline to scheduled time points in:

- Interval history
- Vital signs and weight
- Physical examination findings
- Clinical laboratory evaluations
- Suicidal ideation and behavior assessments
- Concomitant medications

All AEs will be coded using the Medical Dictionary for Regulatory Activities (MedDRA 17.1 or beyond). The incidence and frequency of treatment emergent AEs (occurred after the first dose of study drug) will be summarized by System Organ Class (SOC), Preferred Term (PT), severity, and relationship to treatment. The numbers (frequency) and incidence rates of AEs and SAEs will be summarized by treatment group. A by-subject listing will be provided

for those subjects who experience a SAE, including death, or experience an AE associated with early withdrawal from the study or study drug treatment. Each of these outputs will include tabulation by maximum severity for each SOC and preferred term. Summaries of AEs will be provided in descending order of frequency by SOC and preferred term.

Additional tables summarizing patient incidence (by preferred term) of the following will be generated:

- All AEs;
- SAEs;
- Treatment-related AEs;
- Treatment-related SAEs;
- AEs leading to the discontinuation of study drug or discontinuation of study;
- Deaths.

Separate outputs maybe be provided for subgroups defined by gender, and race (if feasible). Detailed listings for all AEs and listings and/or narratives will be provided for serious and significant AEs, deaths (with “on-study” deaths [deaths that occur before the end of safety follow-up period] identified).

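### For subjects not entering UX001-CL302, the last scheduled safety call may fall on day 28 or 29 after the last dose, 2 days or 1 day before adverse event collection ends

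*Protocol*

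**What the plan says.** **Timing of the call.** Protocol 7.5.1.5 states: "A safety follow-up call should be initiated by the site personnel 28 days (+5 days") after the last dose. Table 2.1 footnote c repeats it: "The site personnel will initiate a safety follow-up telephone call 28 days (+5 days"). The window runs forward only. The call is for completers who do not enter UX001-CL302 and for subjects who discontinue early. Table 2.1 shows no contact after it.

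**AE collection period.** Section 7.5.5.10: "All AEs will be recorded from the time the subject signs the informed consent until 30 days after the last dose of study drug". Section 8.5.4.1: "All AEs will be collected from the time the subject signs the informed consent through 30 days following the last dose of study drug". Both end collection earlier if the subject signs consent for the extension study first.

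**Other contacts.** Table 2.1 footnote b allows more: "Additional unscheduled telephone calls may also occur for subject follow up". For early discontinuers, section 7.5.1.4 says "every reasonable effort should be made to perform the Early Termination Visit procedures within four weeks of discontinuation".

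**Related timing text.** Protocol 7.4.3 places the call at roughly four weeks after the last dose and states: "Individual subject participation in this study will be a maximum of 56 weeks". SAP 3.4 still describes a follow-up visit at 4 weeks. SAP Appendix 10.1 footnote c gives that visit a window of four weeks plus or minus 5 days.

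**The concern.** The protocol fixes the end of AE collection at day 30, but allows its last scheduled question about AEs to be asked before then. A site that calls on the nominal day, day 28, follows the protocol exactly and still has no planned occasion to ask about days 29 and 30. An AE or serious AE starting on those days lies inside the stated collection period, yet is captured only if the subject volunteers it, the site makes an unscheduled call, or the site learns of it another way. What is at stake is complete solicited safety data at the end of follow-up. No efficacy result is touched.

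**Working it through.** The plan gives no figure for this gap. The check is day arithmetic.

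**Inputs**
- Call window: day 28 to day 28 + 5 = 33 after the last dose (Protocol 7.5.1.5; Table 2.1 footnote c).
- End of AE collection: day 30 (Protocol 7.5.5.10 and 8.5.4.1).
- Treatment: 48 weeks. Screening to Baseline: up to 4 weeks (Protocol 7.4.3).
- Visit window: plus or minus 5 days (Protocol 7.5.1.3).

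**Gap for each allowed call day** (30 minus the call day, or zero if negative)

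| Call day | 28 | 29 | 30 | 31 | 32 | 33 |
|---|---|---|---|---|---|---|
| Days not asked about | 2 | 1 | 0 | 0 | 0 | 0 |

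Two of the six allowed days leave a gap. A call on day 30 is counted as zero, although it cannot cover the rest of that day.

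**Relative size**
- Post-dose period: 2/30 = 6.7%.
- On-treatment plus post-dose AE collection: 48 x 7 + 30 = 366 days; 2/366 = 0.55%.

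**Subjects affected.** The documents do not say how many subjects will have the call, or on which day sites will make it. Assume calls spread evenly over the window. If rollover matches Phase 2 (46 of 47; Protocol 5.2.3), 80 x (1 - 46/47) = 1.7 subjects have the call, and 1.7 x 2/6 = 0.6 have a gap. If nobody rolls over, 80 x 2/6 = 26.7 have a gap. Even spread is only a convenience. Day 28 is the nominal day, so the share of calls with a gap could be higher.

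**Participation time**
- Plan's own figure: 4 + 48 + 4 = 56 weeks = 392 days.
- Current call window, on-time Week 48 visit: 28 + 336 + 33 = 397 days (56.7 weeks).
- Current call window, Week 48 visit 5 days late with dosing up to that visit: 28 + 341 + 33 = 402 days (57.4 weeks).
- Call at 30 (+3) days: the latest call is still day 33, so 397 and 402 days do not change.
- Call at 30 (+5) days: 28 + 336 + 35 = 399 days (57.0 weeks) with an on-time visit, 2 days longer than now.

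**The case against.** The strongest reply is that nothing here contradicts anything else. Sections 7.5.5.10 and 8.5.4.1 say how long events are recorded; section 7.5.1.5 says when the last planned call is made. Four of the six allowed days already reach day 30. Unscheduled calls are permitted, safety concerns are followed until the investigator considers them resolved, and deaths through day 30 must be reported within 24 hours of knowledge. For subjects not entering the extension, events after day 30 that may be drug-related are still to be reported. Sialic acid has a circulating half-life under 1 hour (Protocol 5), so day 28 is 28 x 24 = 672 hours, or more than 672 half-lives, after the last dose. SAP 8.9 counts events after the first dose as treatment-emergent and states no 30-day cut-off. All of this stands, and it makes the point minor. It does not supply a scheduled question about days 29 and 30.

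Four stronger readings are tempting, and the documents do not support them:
- **AE collection stops at the call, so later events are lost.** It does not. Collection runs through day 30, and events the site learns of stay reportable.
- **The gap can reach 7 days.** SAP Appendix 10.1 footnote c would allow day 23, and 30 - 23 = 7. But SAP section 3 makes the protocol definitive on design, and the protocol window has no minus side. The SAP text needs aligning; it does not widen the gap.
- **Early discontinuers always share the gap.** If drug and study stop together, an early termination visit made within four weeks falls by day 28. That timing is only a best-effort target, so a later visit could itself cover days 29 and 30.
- **On-study deaths could be misclassified.** SAP 8.9 defines them as "deaths that occur before the end of safety follow-up period" without naming a day. Protocol 8.5.4.2, however, ties the reporting of deaths to the period in 8.5.4.1, which is 30 days. The call date does not move that boundary.

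**Conclusion.** The mismatch is real and minor. For completers not entering UX001-CL302 and for early discontinuers, a compliant call on day 28 or 29 leaves 2 days or 1 day of the AE period without scheduled questioning. The upper limit is 2 days of solicitation per subject. This rests on the protocol's forward-only window governing, and on no later visit or unscheduled call taking place. The number of subjects affected cannot be fixed from the documents. No planned safety conclusion is likely to change; the case for acting is that the sponsor can make the last planned question fit its own collection period without adding a contact.

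**What to change.** Set the call at 30 days (+3 days) after the last dose in Protocol 7.5.1.5 and Table 2.1 footnote c. Bring the matching text into line: the four-week wording in Protocol 7.4.3, the 4-week visit in SAP 3.4, and the plus-or-minus window in SAP Appendix 10.1 footnote c.

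The earliest call then falls on day 30 and the latest stays at day 33, so maximum participation is no longer than now. A call made on day 30 still cannot ask about the remaining hours of that day; this is a far smaller gap than the present one.

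The cost is a call window of 4 days (30 to 33) instead of 6, so somewhat more calls may fall outside it. IRB/EC approval is needed before use (Protocol 8.1.1), so the change should be bundled with the next amendment rather than prompt one of its own.

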7.5.2 Efficacy Measures

Efficacy will be evaluated by changes in upper and lower extremity muscle strength and function, and self-reported physical functioning. Results from baseline assessments will be compared with those of post-treatment assessments listed in the Schedule of Events (Table 2.1), with efficacy conclusions based on change from baseline over the treatment period for the SA-ER treatment group compared to placebo.

The primary efficacy endpoint in this study, UEC as derived from dynamometry, will provide a clinical measure of muscle function and strength. The primary efficacy endpoint will be the change from baseline in UEC score for the SA-ER group compared with placebo based on the overall trend over the treatment period (Section 7.6.4). The primary efficacy measure will be supported by multiple secondary and tertiary endpoints, including GNEM-FAS mobility and upper extremity domain scores, LEC, multiple measures of lower extremity strength and function, clinical performance tests to assess mobility and functional abilities, health-related quality of life assessments, and biochemical markers. Secondary and tertiary endpoints and associated analyses are described in Sections 7.6.4.2 and 7.6.4.3, respectively. The following section describes the assessments that will be performed throughout the study to derive primary, secondary, and tertiary endpoints.

7.5.2.1 Dynamometry

Dynamometry of multiple muscle groups will be used to derive the primary efficacy endpoint as well as multiple secondary and tertiary efficacy endpoints. Dynamometry sessions will occur at each visit beginning with the Screening Visit to serve as training and ensure the subject meets eligibility criteria.

Formal training will be conducted with the clinicians administering dynamometry (preferably a licensed physical therapist) to standardize technique and minimize variability. The maximum voluntary isometric contraction (MVIC) against a dynamometer will be used to measure strength in the following muscle groups: shoulder abductors, elbow flexors, elbow extensors, hip abductors, hip adductors, hip flexors, hip extensors, knee flexors and knee extensors. A hand dynamometer will be used to assess gross grip strength.

Each effort will last approximately three seconds with a slow build to a maximum voluntary force. Strength in the elbow flexors and elbow extensors will be measured with the subject lying in a supine position on an examination table. Strength in the hip extensors will be measured with the subject leaning over an examination table in a prone position. All other muscle groups will be tested with the subject in a sitting position. All measurements will be taken bilaterally; the dominant side will be noted in the CRF. Three tests will be administered in an attempt to obtain two force values within approximately 15% of each other for each muscle group. The total force (in kg) will be recorded at the time of test

administration. The highest force value collected for each muscle group will be used for data analysis. The percent predicted values will be calculated after the testing using published normative data (Mathiowetz et al. 1985); (NIMS 1996); (Bohannon 1997); (Peters et al. 2011). Muscle strength and percent predicted values for each muscle group tested will be analyzed as secondary or tertiary endpoints (Section 7.6.4).

